### **8.5. Replacement of individual subjects after withdrawal**

Subjects will be replaced after the withdrawal.

### **8.6. Follow-up of subjects withdrawn from treatment**

As this trial does not interfere with the standard care, subjects withdrawn from treatment will receive the clinical standard follow up after a prostate cancer biopsy procedure.

## **8.7. Premature termination of the study**

The MRI and TRUS guided prostate biopsies are already performed routinely in clinical care. The extra targeted prostate biopsies are considered to convey minimal additional risk over the systematic biopsy cores that were already planned. Therefore, premature termination of the study based on risk convened to participants is very low. As is mandatory, every serious adverse event will be discussed with the accredited METC. In the case of several adverse events (Grade 3; CTCAE v3.0) caused by mpUS imaging of the prostate with the UCA Sonovue®, the principal investigator can decide in consultation with the accredited METC to terminate the study. The METC and/or CCMO will be informed. After premature termination of the study, subjects will still receive the standard clinical treatment or follow-up for prostate cancer.

## **9. SAFETY REPORTING**

### **9.1. Ultrasound and ultrasound contrast agent**

Ultrasound is considered a safe diagnostic tool because of the use of non-ionizing radiation. In general, few side-effects are attributed to ultrasound microbubble contrast agents. Complications like nephrotoxicity, which can occur with iodine containing contrast media in use for CT, have never been reported. Adverse events of microbubble contrast media appear to be transient, mild and rare [38,39,40]. The most frequently mentioned minor side-effects of microbubble contrast agents are transient alteration of taste, local pain at the injection site and facial or general flush (1-5%) [41]. Serious adverse events, which consists of hypersensitivity allergic reactions, are rare (<0.01%) [42]. Because the gaseous content of the microbubble agents is eliminated by the lungs, it is of importance to evaluate whether impaired pulmonary function could be a contraindication for the use of microbubbles. In a study with SonoVue® (Bracco, Geneva) in patients with Chronic Obstructive Pulmonary Disease, CEUS appeared to be as safe and well tolerated as in a healthy control group [38]. The Committee for Medicinal Products for Human Use (CHMP) has granted SonoVue® a marketing authorization, but it should not be used together with the medicine dobutamine and in pregnant or breastfeeding women ([www.emea.eu](http://www.emea.eu)).

### **9.2. Temporary halt for reasons of subject safety**

In accordance to section 10, subsection 4, of the WMO, the sponsor will suspend the study if there is sufficient ground that continuation of the study will jeopardise subject health or safety. The sponsor will notify the accredited METC without undue delay of a temporary halt including the reason for such an action. The study will be suspended pending a further positive decision by the accredited METC. The investigator will take care that all subjects are kept informed.

### **9.3. AEs, SAEs and SUSARs**

#### **9.3.1 Adverse events (AEs)**

Adverse events are defined as any undesirable experience occurring to a subject during the study, whether or not considered related to [the investigational product / trial procedure/ the experimental intervention]. All adverse events reported spontaneously by the subject or observed by the investigator or his staff will be recorded.

#### **9.3.2 Serious adverse events (SAEs)**

A serious adverse event is any untoward medical occurrence or effect that

- results in death;
- is life threatening (at the time of the event);
- requires hospitalisation or prolongation of existing inpatients' hospitalisation;
- results in persistent or significant disability or incapacity;
- is a congenital anomaly or birth defect; or
- any other important medical event that did not result in any of the outcomes listed above due to medical or surgical intervention but could have been based upon appropriate judgement by the investigator.

An elective hospital admission will not be considered as a serious adverse event.

Excessive hematuria, acute urinary retention, prostatitis, hospitalization due to prostatitis and/or urosepsis will be recorded but not considered as SAE, as these adverse events are attributed to the regular prostate biopsy procedure and are not expected to be aggravated or occur more frequently due to participation in this study.

Emergency contact details for reporting serious adverse events and serious adverse device effects:

[name]

[name]

[contact]

The sponsor will report the SAEs through the web portal *ToetsingOnline* to the accredited METC that approved the protocol, within 7 days of first knowledge for SAEs that result in death or are life threatening followed by a period of maximum of 8 days to complete the initial preliminary report. All other SAEs will be reported within a period of maximum 15 days after the sponsor has first knowledge of the serious adverse events.

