## 5. TREATMENT OF SUBJECTS

### 5.1. Investigational treatment

In this study, all men will undergo both MRI and PCaVision imaging. Two different specialists will perform these imaging who are unaware of the results of the other imaging technique.

MRI images will be read by an experienced uro-radiologist and suspicious lesions will be marked. An experienced urologist will read the PCaVision images and mark suspicious lesions. This will ensure that suspicious lesions will be identified based on each imaging technique independently (i.e., blinded for the other imaging technique).

A MRI targeted 3-core biopsy per lesion (with a maximum of 2 lesions) and/or a PCaVision targeted 3-core biopsy per lesion (with a maximum of 2 lesions) will be performed by a urologist if suspicious lesions have been identified based on imaging. The maximum number of targeted biopsies per imaging technique is 6. Each biopsy sample will be collected in a separate container. As a result, there will be maximally 6 containers with samples from the PCaVision targeted biopsy, and 6 containers with samples from the MRI targeted biopsy.

If no suspicious lesions have been identified by an imaging technique, no targeted biopsies based on that imaging technique will be performed. It is up to the local physician whether routine systematic biopsies will be taken.. If suspicious lesions have been identified with both PCaVision and MRI in the same patient, the order of the targeted biopsies will be randomized. Randomization of the order will prevent any systematic advantage of performing the targeted biopsies of one imaging technique always before the other technique.

Moreover, if the clinician suspects that the same lesion has been identified by both PCaVision and MRI, both PCaVision and MRI targeted biopsies of this lesion will be performed. This event will be documented. The outcome of the evaluation of the collected samples obtained by both PCaVision and MRI targeted biopsies will be compared to ensure that there is no deviation in outcome resulting from the order of targeting the same lesion. It is up to the local physician whether routine systematic biopsies will be taken beside these target biopsies. All biopsies will be performed in a single visit.

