## **5.3. Follow up Activities**

After completion of the biopsy procedure(s), it is expected that the only complications possibly experienced by the study participants encompass the adverse events that are related to the biopsy procedures. From clinical practice it is known that these events will

manifest within 2 weeks, and will be resolved within 6 weeks. If there are no complications within 2 weeks, the patient is considered to have completed the study. The study will be closed when all patients have completed the study, with a maximum follow-up of 6 weeks if complications occur.

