### 10.1. Primary study endpoint analysis

The main analysis is the comparison of the detection rate of clinically significant cancer (defined as GG $\geq$ 2) between the PCaVision targeted biopsy pathway and the MRI targeted pathway. We will calculate the difference in these detection rates and its corresponding 97.5% confidence interval. Because of the paired design of our study, we will use the approach of Liu which accounts for the correlation between the detection rates of both pathways [44,45,46]. A one-sided 2.5% equivalence test will be performed to formally evaluate whether the lower bound of the confidence interval will not exceed the non-inferiority margin specified at an absolute difference in detection rates of 5%.

As a secondary analysis, the comparison of the proportion of men in whom targeted biopsies could have been safely omitted in the PCaVision pathway compared to the MRI pathway.

This ~~10.2. Secondary study endpoint analysis~~ with respect to detection rate (see above) does not come at the price of fewer patients in whom targeted biopsies can be prevented (e.g., more unnecessary targeted biopsies). For PCaVision this proportion is the number of men in whom there are no lesions to be biopsied based on PCaVision while the MRI biopsy strategy and systematic biopsy (when performed) did not detect clinically significant cancer divided by the total number of men in the study. Likewise, this proportion for MRI is defined as the number of men in whom there are no lesions to be biopsied based on MRI while the PCaVision biopsy strategy and systematic biopsy (when performed) did not

detect clinically significant cancer divided by the total number of men in the study. Given the fully paired nature of the design, the proportions will be tested for being statistically significance different using the McNemar test (two-sided alpha of 5%). The approach of Liu which accounts for the correlation [44,45,46] will be used to calculate a 95% confidence interval for the difference between these proportions.

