Risks associated with participation in clinical study	Additional targeted biopsies could be performed because of the identification of PCa based on PCaVision imaging. These extra biopsies carry a small risk of haemorrhage and infection.
Possible interactions with concomitant medical treatments	There are no interactions with concomitant medical treatments
Steps that will be taken to control or mitigate risks	Risk are mitigated by specific mitigation actions as defined in the Risk Analysis File. For the 6 medium-level risks that were mitigated to low-level risk, adequate training and/or supervision of the operator, and detailed instructions in PCaVision 1.0's IFU were the most often mentioned mitigation actions.
Risk-to-benefit rationale	
The investigational device "PCaVision 1.0" has individual residual risks that are all acceptable and reduced as far as possible without introducing new risks or modifying the probability or severity levels of already defined risks.
 
During the clinical investigation, the patient will receive standard of care and there will be no diagnosis nor clinical decisions based on the output of PCaVision, the diagnosis is always based on the outcome of the biopsy results. Therefore, the investigational device will not contribute to any hazardous situation that could result in unacceptable risk after implementing risk control measures.
 
There could be a potential benefit for the patients participating in this study when a clinically significant cancer is detected by targeted biopsies based on PCaVision that would otherwise have been missed by both MRI and (potentially) systematic biopsies. However, even in the case where the patient do not receive immediate clinical benefit, the results of this study may be important for future patients suspected of prostate cancer. If PCaVision is sufficiently accurate, it could replace MRI as the central imaging strategy which would lead to a more streamlined and more cost-effective diagnostic work-up as the ultrasound examination is less costly and can be performed by urologists followed by targeted biopsies in the same session. If PCaVision is sufficiently sensitive, systematic biopsies after a negative ultrasound examination could even be omitted in the future, thereby reducing the burden associated with unnecessary biopsies.

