None of the previous trials performing prostate imaging with CEUS reported procedure- or device-related adverse events. Apart from the aforementioned risks related to the

administration of contrast ultrasound there are no anticipated additional risks for participants in this study. The risk is negligible (“verwaarloosbaar risico”).

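### The SAE exemption for biopsy complications rests on grounds that fail for men whose only biopsy is PCaVision-targeted

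*Combined protocol and SAP*

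**What the plan says.** Section 9.3.2 gives the usual seriousness criteria, including death, threat to life and hospitalisation. It then takes four items out of SAE status: excessive haematuria, acute urinary retention, prostatitis, and hospitalisation for prostatitis and/or urosepsis. Two grounds are given. The events are "attributed to the regular prostate biopsy procedure", and they "are not expected to be aggravated or occur more frequently due to participation in this study". SAEs go to the METC within 7 days if fatal or life-threatening and within 15 days otherwise. Section 8.7 adds that every SAE is discussed with the METC.

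On who is biopsied, section 5.1 says that a technique showing no lesion leads to no targeted biopsy for that technique, and that "It is up to the local physician whether routine systematic biopsies will be taken". The Summary (burden and risks) describes local practice as ranging from systematic biopsy in everyone, through only men with an MRI lesion, to none. Section 5.1 also classes the PCaVision-targeted biopsy as additional to standard care.

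On risk, the table in section 13 has a row headed "Risks associated with participation in clinical study", which states: "These extra biopsies carry a small risk of haemorrhage and infection". The Summary and section 11.3 say the same. The closing text of section 13 says that, apart from contrast-related risks, "there are no anticipated additional risks for participants in this study".

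**The concern.** The exemption presumes that every participant has a regular biopsy to which a complication can be attributed. The design does not guarantee this. A man may be biopsied solely because PCaVision showed a lesion. If he is then admitted with urosepsis, the event arose from a study procedure, yet section 9.3.2 as written keeps it out of SAE reporting.

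This matters because section 5.3 expects that, after the biopsy, "the only complications possibly experienced by the study participants encompass the adverse events that are related to the biopsy procedures". The exemption therefore falls on the kind of event the protocol foresees at that stage. The independent oversight at stake is that of the METC: section 9.5 provides for no DSMB, and the specific termination trigger in section 8.7 concerns events caused by imaging with the contrast agent, not by biopsy.

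**Working it through.** No figure in the plan is in dispute. The check sets the grounds of the exemption against the biopsy pathways that the protocol allows.

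**Step 1: which men have a regular biopsy?** Inputs: 3 cores per lesion and at most 2 lesions per technique (Summary, section 8.2), so one technique gives 1 × 3 = 3 or 2 × 3 = 6 cores.

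| Pathway | Biopsy without the study | Added by PCaVision |
|---|---|---|
| MRI-targeted biopsy done | 3 or 6 targeted cores, plus any local systematic cores | 0, 3 or 6 |
| No MRI-targeted biopsy; systematic biopsy done | Local systematic cores | 0, 3 or 6 |
| No MRI-targeted biopsy; no systematic biopsy; PCaVision lesion | **None** | **3 or 6** |
| No lesion on either; no systematic biopsy | None | 0 |

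The third row is possible at any centre that takes no systematic cores in MRI-negative men, which covers two of the three local practices in the Summary. The analysis plan allows for it too. In section 10, the MRI proportion of safely omitted biopsies counts men with "no lesions to be biopsied based on MRI while the PCaVision biopsy strategy and systematic biopsy (when performed) did not" detect significant cancer. That allows for a man without an MRI lesion who has a PCaVision biopsy, with systematic biopsy only where it was done.

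**Step 2: ground one, attribution to the regular biopsy.** In the first two rows there is a regular biopsy, so attribution is at least possible. In the third row there is none. The premise in section 8.7, that the extra cores come on top of systematic cores that would be taken anyway, also has nothing to refer to in this man.

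**Step 3: ground two, no increase through participation.** In the first two rows, a small added risk can coexist with an expectation of no noticeable increase; this is a tension and no more. In the third row the comparison is no biopsy against 3 or 6 cores. Any biopsy complication there is due to participation, which is how section 13's table classifies the bleeding and infection risk.

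**Step 4: what the exemption removes.**
- Kept: recording (sections 9.3.1 and 9.3.2), follow-up until resolved or stable (9.4), up to 6 weeks of follow-up if complications occur (5.3), three-monthly monitoring (12.2), the sponsor's duty to suspend for safety (9.2), and an annual METC report that includes other problems (12.4).
- Lost: for a hospitalised, non-life-threatening case, the 15-day METC report and the METC discussion in section 8.7. If fatal or life-threatening cases are also read as exempt, the 7-day report is lost as well.

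**The case against.** The strongest reply is that the regular biopsy in section 9.3.2 means the type of procedure. Section 8.7 opens by noting that MRI- and TRUS-guided biopsies are routine care, so the exemption would cover known complications of an ordinary technique whatever the indication. This is a fair reading of ground one, but it does not rescue ground two: a routine technique applied to a man who would otherwise have had no biopsy still adds risk through participation.

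Ground two could instead be read as a statement about the study as a whole. If few men are affected, the overall frequency may hardly change. That is reasonable as an expectation, but SAE status is decided event by event, and it gives no reason to withhold a report on an event that the study biopsy caused.

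Other objections stand in part. The conflict between the closing sentence of section 13 and the table above it is mainly loose drafting, since the biopsy risk is disclosed in three places. Making SAE status depend on biopsy indication gives sites an extra step, though they already need to know which targeted procedures each man had.

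A reader might try to size the group. The introduction's illustrative MRI figures give (259 + 27)/1000 = 28.6% MRI-negative, or 0.286 × 438 ≈ 125 men. This is neither an estimate nor an upper bound. The documents do not give the PCaVision-positive share of these men or the number of centres that omit systematic biopsy. Men with inadequate MRI (section 4.5) might also be biopsied on PCaVision alone, and section 10.3 allows the 438 to rise. No complication rate is given for biopsied men.

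**Conclusion.** The point holds for one subgroup: men whose only biopsy is PCaVision-targeted. For them neither stated ground supports the exemption, unless ground one is read as referring only to the type of procedure; ground two fails on either reading. For men biopsied anyway there is only a tension.

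The number of men and events cannot be computed from the documents. It may be zero, if every centre takes systematic cores in MRI-negative men. My judgement that it is probably small rests on several conditions having to coincide and on the protocol's own description of the risk as small.

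Three stronger readings are not supported:
- That safety data are lost or an endpoint is biased. The events are recorded and followed up, and no endpoint or sample size depends on their classification.
- That fatal or life-threatening cases, or admissions for haematuria or retention, are clearly exempt. The text has no exception for the former and names hospitalisation only with prostatitis and/or urosepsis, so both are ambiguous.
- That the exemption explains the absence of a DSMB. Section 9.5 justifies that separately, by minimal risk.

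The change is worth making. As written, the rule can keep a serious event caused by the study from prompt ethics-committee review, and it is cheap to correct.

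**What to change.** 1. In section 9.3.2, state that the exemption does not apply to an event meeting that section's own seriousness criteria in a man whose only biopsy was PCaVision-targeted. Such events follow the existing 7- and 15-day timelines.
2. State there that fatal or life-threatening cases of the listed events remain reportable in all participants.
3. Reconcile the rationale in sections 8.7 and 9.3.2 and the closing text of section 13 with the Summary, section 5.1, section 11.3 and the section 13 table.

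Optionally, tabulate the recorded post-biopsy infection, retention and bleeding by indication (MRI only, PCaVision only, both; with or without systematic cores).

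Cost: a protocol amendment notified to the METC under section 12.3, site instruction, and a probably small number of additional SAE reports. The optional table uses events already recorded. Sample size and efficacy analysis do not change.

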### **9.3.3      Device deficiency**

Device deficiencies are defined as inadequacy of a medical device with respect to its identity, quality, durability, reliability, usability, safety or performance. These events are reported to the study manager (principal investigator) who shall report these to the accredited METC and manufacturer and assess reportability to Competent Authorities.

### **9.4. Follow-up of adverse events**

All AEs will be followed until they have abated, or until a stable situation has been reached. Depending on the event, follow up may require additional tests or medical procedures as indicated, and/or referral to the general physician or a medical specialist. SAEs need to be reported till end of study within the Netherlands, as defined in the protocol.

### **9.5. Data Safety Monitoring Board (DSMB)**

Since participants will receive standard of care, with additional biopsies based on PCaVision for this study which can be considered of minimal risk and without infringement in clinical decision making, no DSMB will be established.

## 10. STATISTICAL ANALYSIS

In the analyses, we will compare the histological findings from two main diagnostic pathways: (1) PCaVision imaging in all men followed by targeted biopsies in men with suspicious lesions; (2) MRI imaging in all men followed by targeted biopsies in men with suspicious lesions. The findings will be analysed and reported at the per-patient rather than per-lesion level because the per-patient level of reporting has the greatest clinical relevance. In the analysis, we differentiate between the following two datasets:

- Total study population, all men included in the study to undergo PCaVision and MRI imaging.
- Paired dataset with sufficient quality images and subsequent targeted biopsies for both PCaVision and MRI.

The last dataset will be used in the paired analysis when comparing the diagnostic accuracy of different imaging pathways.

In the descriptive part of the analysis we will show the cross- tabulation of histological findings (ranging from no cancer, GG=1 to GG=5) comparing the two main diagnostic pathways: PCaVision based targeted biopsies against MRI based targeted biopsies.

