#### **4.5. Sample size calculation**

The sample size calculation is based on demonstrating non-inferiority between the detection rate of clinically significant cancer from the PCaVision pathway and the MRI pathway using patients as the unit of analysis and data from the fully paired design.

The detection rates of PCa (GG $\geq$ 2) based on MRI and PCaVision targeted biopsies are expected to be around 30%. These values are based on the detection rates of PCa (GG $\geq$ 2) reported by Mannaerts et al., 2020 [30] and Grey et al., 2022 [43], which were found to be 29% and 30% with MRI and 28% and 26% with 2D CUDI (older version of PCaVision), respectively.

The non-inferiority margin is set to 5% absolute difference in detection rate. The expected proportion of discordant pairs is 10%. This proportion expresses the degree in which PCaVision and MRI disagree with respect to detecting and missing significant cancers in a paired design. This parameter is relevant when analysing data from a paired study design. A smaller percentage of discordant pairs will lower the required sample size. In the studies of Mannaerts et al., 2020 [30] and Grey et al., 2022 [43], the percentage discordant pairs were 10.1% and 8.9%, respectively.

Our assumptions of the sample size calculations are therefore the following: an expected detection rate of 30% for both imaging techniques, a non-inferiority margin of 5% points and a percentage discordance between both imaging techniques of 10%, a one-sided type 1 error of 2.5% (as recommended by the European Medicines Agency) and a power of 80%. This leads to a required total sample size of 350 patients.. This is the total number of men who need to undergo both PCaVision and MRI, and produce images of sufficient quality, followed by targeted biopsies if indicated. This sample size calculation was performed according to Liu et al., 2002 [47] and Hintze, 2008 [48].

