With both imaging pathways, we expect a certain percentage of men in whom either PCaVision or MRI or both produce image quality that is insufficient to perform targeted biopsies upon, or technical issues when performing targeted biopsies. The primary, paired analyses will be based on men having sufficient quality images and targeted biopsies from both imaging techniques. During the development of the PCaVision algorithm, insufficient scans were manually excluded to ensure optimal quality for training purposes. Currently, PCaVision incorporates an automated image quality check to guarantee sufficient signal and quality. To compensate for discarded scans due to quality issues, 25% additional patients will be included. The total sample size will therefore be 438 subjects to obtain 350 evaluable patients in the paired analysis.

As we would like to include PCa patients from 5 clinical centres, the patient number target per centre is 80, with a range of 40-120.

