### 8.2. Randomisation, blinding and treatment allocation

All patients will undergo both PCaVision and MRI imaging before the scheduled biopsy appointment (fully paired diagnostic accuracy design). The MRI – based biopsy targets and PCaVision - based biopsy targets are appointed independently from, and blinded for each other by 2 specialized readers.

After the imaging has been recorded, 0 to 2 different biopsies procedures are performed:

- (1) a maximum of 6 targeted biopsies in maximum 2 different lesions are taken by one physician, from the MRI lesions delineated by the radiologist. The following biopsy approach is used. When 1 suspicious lesion has been identified, 3 targeted biopsies

will be taken. When 2 lesions have been identified, 3 targeted biopsies will be taken per lesion, so 6 biopsies in total. In case 3 or more suspicious lesions have been found, 2 lesions will be selected based on: (1) PI-RADS and (2) size. Consecutively, 3 targeted biopsies will be taken from these 2 selected lesions. So, the maximum number of targeted biopsies per imaging technique is 6. The physician is blinded for the PCaVision results. When there are no suspicious lesions identified on MRI, this biopsy will not be performed.

(2) a maximum of 6 targeted biopsies in maximum 2 different lesions are also taken by this same physician from the lesions identified on PCaVision by the CEUS expert. The same biopsy approach as for MRI is used. When 1 suspicious lesion has been identified, 3 targeted biopsies will be taken. When 2 lesions have been identified, 3 targeted biopsies will be taken per lesion, so 6 biopsies in total. In case 3 or more suspicious lesions have been found, 2 lesions will be selected based on: (1) severity indication and (2) size. Consecutively, 3 targeted biopsies will be taken from these 2 selected lesions. So, the maximum number of targeted biopsies per imaging technique is 6. The physician is blinded for the MRI results and the systematic biopsy approach and outcomes. When there are no suspicious lesions identified on PCaVision, this biopsy will not be performed.

When suspicious lesions have been identified on both PCaVision and MRI, the targeted biopsy procedures are performed in a randomized order by applying block randomization (with block sizes varying between 6 and 10) using a computer-generated list, to prevent potential bias by post-biopsy haemorrhage.

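### The primary paired analysis set is defined inconsistently: read literally it keeps only men with lesions on both techniques, while the sample size and pathway definitions need men without a lesion to be kept

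*Combined protocol and SAP*

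**What the plan says.** Section 10 names two datasets, the total study population and a "Paired dataset with sufficient quality images and subsequent targeted biopsies for both PCaVision and MRI". It adds: "The last dataset will be used in the paired analysis when comparing the diagnostic accuracy of different imaging pathways". Section 4.5 says the same of the primary endpoint: "The primary, paired analyses will be based on men having sufficient quality images and targeted biopsies from both imaging techniques".

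Section 5.1 sets the biopsy rule: "If no suspicious lesions have been identified by an imaging technique, no targeted biopsies based on that imaging technique will be performed". Section 8.2 accordingly allows that "0 to 2 different biopsies procedures are performed" per man.

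Two other statements describe a wider population. Section 4.5 says the 350 are men who have both imaging tests "and produce images of sufficient quality, followed by targeted biopsies if indicated". Section 10 opens by defining the experimental pathway as "PCaVision imaging in all men followed by targeted biopsies in men with suspicious lesions", with a matching definition for MRI.

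**The concern.** Take a man with two good scans, a lesion on MRI and nothing on PCaVision. He has an MRI targeted biopsy and, by design, no PCaVision targeted biopsy. He fails the paired-set definition in sections 4.5 and 10, yet he counts towards the 350 under the if-indicated wording in section 4.5. The same applies to a man with a lesion on PCaVision only, and to a man with no lesion on either technique.

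If the MRI biopsy of the first man shows GG ≥2 disease, he is a discordant pair against PCaVision. The trial exists to count such pairs. An analysis set that requires biopsies from both techniques removes every discordant pair of this type, in both directions, and keeps only those where both techniques marked a lesion and one set of cores missed the cancer. The primary population would then depend on which sentence the analyst follows, possibly after the data have been seen.

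**Working it through.** **1. The plan's own figure.** Inputs from section 4.5: margin 0.05, one-sided alpha 2.5%, power 80%, equal detection rates, 10% discordant pairs (0.05 in each direction). The score-type formula for paired proportions is

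n = [z(0.975)·√v0 + z(0.80)·√v1]² / 0.05².

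Here v1 = 0.05 + 0.05 = 0.10. Under the null difference of −0.05 the constrained discordant probabilities are 0.0345 and 0.0845, so v0 = 0.0345 + 0.0845 − 0.05² ≈ 0.1164. The result is n = 349.6, that is 350. The simpler Wald form gives 314 and does not match. Inflation: 350 × 1.25 = 437.5, that is 438. The plan's numbers reproduce with a 10% discordance taken over all men with two adequate scans.

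**2. Can the literal set reach 350?** The 25% inflation is given for scans discarded on quality; 350/437.5 = 80% of men remain. To have 350 men with biopsies from both techniques, every one of those remaining men would need a lesion on both.

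Section 1 quotes 273 true and 441 false positives per 1000 men for MRI at 30% prevalence, an MRI-positive share of 714/1000 = 71.4%. Then:

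- of 350 evaluable men, at most 0.714 × 350 = 250 have an MRI targeted biopsy;
- of all 438, with no quality losses, at most 0.714 × 438 ≈ 313;
- reaching 350 would take at least 350/(0.714 × 0.80) ≈ 613 enrolled.

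These are upper limits on the set and a lower limit on enrolment, because a PCaVision lesion is required as well.

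**3. Effect on the result: an illustration.** Taken from the documents: prevalence 30%, MRI sensitivity 0.91 and specificity 0.37 (section 1), PCaVision specificity 0.55 (the 2D figure in sections 1 and 6.2.1). Assumed: PCaVision sensitivity 0.70, conditional independence, and a 3% chance per technique that the cores miss a marked cancer. Simulation with 350 men with adequate images and a score test.

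- True pathway difference: 0.30 × 0.97 × (0.70 − 0.91) = −6.1 points, which is outside the margin.
- Share positive on both: 0.30 × 0.91 × 0.70 + 0.70 × 0.63 × 0.45 = 0.191 + 0.198 = 0.390, about 136 men.
- Expected difference among those men: zero, because the targeting misses are equal.

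| Targeting misses (MRI / PCaVision) | True difference | Difference, both-positive set | Non-inferior, both-positive set |
|---|---|---|---|
| 3% / 3% | −6.1 | 0 | about 75% |
| 10% / 10% | −5.7 | 0 | about 42% |
| 3% / 10% | −7.6 | −3.4 | about 8% |

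With all men with adequate images, the first row gives about 0.6%. Arithmetic for the other rows: 0.30 × 0.90 × (0.70 − 0.91) = −5.7; 0.30 × (0.70 × 0.90 − 0.91 × 0.97) = −7.6; and (0.191/0.390) × (0.90 − 0.97) = −3.4.

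**4. Direction is not fixed.** Assume PCaVision-only detection of 2% and MRI-only detection of 10%, a true difference of −8 points. If half the discordance comes from unmarked lesions, −4 points remain. Divided by a both-positive share of 60% this is −6.7 points; divided by 40% it is −10 points. With 75% or 100% of discordance from unmarked lesions and a 60% share, the restricted difference is −3.3 or 0.

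**The case against.** The strongest reply is that the wording has a natural inclusive reading. Sufficient quality may govern both images and biopsies, so the requirement would exclude only failed scans and failed biopsies. Sections 8.1.2 and 10.2 use the mirror phrase, treating inadequate targeted biopsies as a quality failure. The sentence in section 4.5 just before the definition gives image quality and technical biopsy problems as the sources of loss, and section 8.4 excludes from analysis on the same grounds. No section lists absence of a lesion as a reason for exclusion. The safely-omitted endpoint needs men without a lesion, and the 30% detection rate rests on whole-cohort figures such as 41/142 and 40/142.

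This stands as evidence of intent. It does not settle the rule: both sentences that define the set ask for biopsies from both techniques, and no sentence says that a man with adequate images and no lesion stays in and counts as not detected.

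The reply also limits the size. The 0.55 specificity belongs to the 2D method and, judging by the title of its reference, to a prostatectomy-correlation study, so it may not be a per-man figure for this device. The 0.70 sensitivity and the targeting misses are assumptions.

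**Conclusion.** The inconsistency is real and concerns the primary population of a non-inferiority claim. Followed literally, the definition in sections 4.5 and 10 contradicts the plan's own 350/438, drops cancers missed because one technique marked nothing, and no longer estimates the difference between pathways. The inclusive reading is probably what is meant.

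The conflict in wording needs no outside figures. The ceiling of about 313 rests on the 71.4% MRI-positive share carrying over to this trial. The error rates of about 75%, 42% and 8% are illustrations under assumed inputs and should not be read as predictions.

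A reader might go further and infer that these men will be dropped, that the restricted difference goes to zero whatever PCaVision's sensitivity, or that misses arise mainly from unmarked lesions. The documents support none of these. The other text points to keeping the men; the zero depends on equal targeting misses; and the source of discordance is not reported. The restricted difference can be smaller or larger than the true one.

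**What to change.** In sections 4.5 and 10, replace the definition of the paired set with: *men with sufficient-quality images from both techniques in whom targeted biopsies were completed for every technique that showed a suspicious lesion; a technique showing no lesion counts as not detecting csPCa.*

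This agrees with the if-indicated wording in section 4.5 and with the pathway definitions in section 10. The cost is one sentence in two places. It needs no new data, patients or procedures, and 350 evaluable and 438 enrolled are unchanged (80.0% power by the score formula at 350). It should be settled before the paired results are examined.
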